These activities will be supported by [name] who can also draw upon the advice of the patient and public involvement steering group of the Nottingham Biomedical Research Centre hearing theme, an experienced panel of patients with extensive knowledge of public involvement methodology and practice.

All public and patients involved can opt to attend training, as available, related to patient involvement in research through the regional network of PPI training, Sharebank, which is also co-ordinated by [name].

A code of conduct will be established for all groups and committees that include patient involvement and develop lay role profiles to ensure the scope and nature of patient roles in the conduct and oversight of the trial are clear and accessible.

Public members involved will be offered honorary payments, in line with PPI payment policies of the NIHR National Centre for Engagement and Dissemination and the NIHR Nottingham Biomedical Research Centre hearing theme. Reasonable expenses will also be offered.

TRIAL FINANCES

Funding source

The trial is funded by a research grant from Cochlear™ Ltd, a company who make the cochlear implant devices which will be used in the trial. The trial is Sponsored by the University of Nottingham and is being conducted independently of the company.

Researchers from the University of Nottingham and NHS clinicians developed the proposal for the research, in consultation with the Company. A contract was put into place between funder and the research team stipulating that from grant activation date the company will not be involved in the running, oversight or data analysis of the trial. The researchers will provide update reports to the funder, as per the agreed schedule laid out in the contract between the two parties.

Participant stipends and payments

Participants will not be paid to participate in the trial, though participant travel expenses will be reimbursed. As a token of appreciation for participating in a trial of such long duration, trial-branded gifts with a low monetary value (e.g., pens) and/or vouchers for high-street or online shopping will be given to participants periodically throughout the trial, up to a maximum value of £50 per participant over 18 months of participation.

Appendices

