Outcome measures	
Primary Outcome: The primary outcome will be a measure of speech understanding; the perception of phonemes as quantified by the phoneme score on the AB word test presented at 60 dBA, in the best-aided condition (i.e., using the devices that the participant considers will help them hear as well as possible), at 9 months post first treatment activation (intervention arm: first CI activation; comparator arm: first HA fitting/optimisation) measured by independent blinded assessors.
 
Secondary Outcomes: Clinical:
 
 - Phoneme perception (AB Word test) (same test as primary outcome but assessed live by audiologist at 3, 6 and 9 months) - Word perception (AB Word test) - Sentence perception in quiet (BKB sentence test) - Sentence perception in noise (BKB sentence test) - Device usage (device logging) - Audiometric thresholds (aided and unaided) 
Clinical measures will be administered in the best-aided condition (i.e., using the devices that the participant considers will help them hear as well as possible), except for unaided audiometric thresholds which will be measured without any devices being worn.
 
Clinical measures will be administered at baseline and at 3, 6, and 9 months post first treatment activation.
 
Patient-Reported:
 
 - Difficulty with listening (SSQ12 scale) - Listening effort and fatigue (EAS, FAS and LEQ-CI*) - Tinnitus severity (TFI) - Tinnitus loudness (VAS-L) - Mood (HADS) - Hearing-specific quality of life (NCIQ, YBHRQL and HHIA) - Health-related quality of life (EQ-5D-5L, HUI3, and ICECAP-A) - Global ratings of change: At each follow up appointment following first treatment activation, participants will be asked to indicate on 7-point Likert scale ranging from 'Much Worse' to 'Much Improved' whether hearing and quality of life have improved or worsened relative to two anchor points: (1) immediately prior to first treatment activation; and (2) since the last trial appointment. - Device usage (participant self-report)

[figure not shown]

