There is no planned interim analysis of treatment efficacy and no formal stopping rules. The Data Monitoring Committee (DMC) and Trial Steering Committee (TSC) will have ongoing oversight of the safety and feasibility of delivery of the trial. The DMC will also review data to ensure the trial has sufficient power to detect a clinically important difference between the two groups.

Randomisation and Blinding

Before randomisation can take place, a series of eligibility assessments need to take place to ensure the potential participant is suitable for all trial interventions. Consent is received prior to eligibility assessment and reconfirmed prior to randomisation. Randomisation cannot take place until a CI surgeon with delegated responsibility has confirmed the potential participant is eligible, following agreement from the MDT.

Randomisation

After reconfirmation of consent and recording of baseline measures, randomisation will take place at the trial site.

Participants will be assigned to treatment groups in a 1:1 ratio, using a concealed, secure internet-based randomisation system developed and maintained by the NCTU. The system will use a minimisation algorithm including a random component, with the following variables and levels: participating site; severity of tinnitus (Tinnitus Functional Index (TFI) score mild (0-28), moderate - significant problems (29-65), and severe (≥ 66)); AB word test phoneme score at 70 dBA $< 50\%$ and $\geq 50\%$. Participants that report no tinnitus will be given a score of 0 which falls under 'mild' tinnitus within the TFI. Access to the randomisation system will be granted to site staff by the NCTU in accordance with the roles delegated by the local Principal Investigator (PI) as documented on the delegation log.

Following randomisation, the participant's GP will also be informed that the participant is taking part in the trial by post.

Blinding

Participants, clinicians and treating staff cannot be blinded to the treatment allocation due to the requirement for some participants to undergo a surgical procedure to receive a CI and the obvious visible differences between a CI speech processor and a HA. However, to minimise bias, the baseline and 9-month measures of the primary outcome will also be video recorded and scored by two independent blinded assessors whose score will be that used in the primary outcome analysis.

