The independent assessors will be qualified audiologists with experience of administering and scoring clinical speech perception tests in patients with severe hearing losses. These independent assessors will be blinded both to treatment arm and timepoint of the recordings. Disagreement in scores will be resolved by consensus between the two assessors, failing which a third assessor will adjudicate. The full procedures for the blinded assessment of primary outcomes will be documented in a separate working practice document, finalised prior to any baseline or primary outcome recording of the AB word test. The blinded scoring of the primary outcome at baseline and 9 months will form part of the trial datasets for analysis.

The trial and data management staff at NCTU will have access to all data in the eCRF to undertake central monitoring. Only the trial management team at the NCTU will have access to the raw footage for the blinded assessments to perform quality control checks (i.e., ensuring the device cannot be seen in the video footage for blinded assessment).

The trial statisticians and TSC members will be blinded to participant group allocations until after database lock; aggregate data will be viewed for trial monitoring purposes only. The Chief Investigator will remain blinded to treatment allocation overall however this is not possible for participants recruited at his site since he is responsible for their clinical care. The Chief Investigator may need to be unblinded in instances where this is required for full causality assessment of serious adverse events (SAEs). Any data summaries and analyses which require knowledge of the treatment allocation (e.g., within the closed report for the DMC) will be conducted by a statistician who is independent of the trial. Such summaries and analyses will be held in an area which is accessible only to the statistician(s) who are independent of the trial. The Chief Investigator will also remain blinded to primary outcomes.

Maintenance of randomisation codes and procedures for breaking code

The randomisation algorithm will be held on a secure, access-restricted system, to which only NCTU database programmers have access. The allocation will be concealed using a secure web-based system developed and maintained by the NCTU. As this is an unblinded trial, no emergency unblinding processes are necessary.

TRIAL MANAGEMENT

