The primary outcome will be a measure of speech understanding, the perception of phonemes as quantified by the phoneme score on the AB word test (Boothroyd, 1968) presented at 60 dBA, in the best-aided condition (i.e., using the devices that the participant considers will help them hear as well as possible), at 9 months post first treatment activation (intervention arm: first CI activation; comparator arm: first HA fitting/optimisation) measured by independent

blinded assessors. Each stimulus will be presented once from a loudspeaker and participants will be instructed to repeat as much of each word as they could hear, even if they only heard part of the word and even if the word does not make sense to them. No time limit will be placed on participants to respond to each stimulus. The test will be administered by a qualified audiologist, who will proceed to present each stimulus only when the participant is facing the loudspeaker and is attentive.

The test will be scored live by the audiologist administering the test at all timepoints with no feedback given to the participant at any point in the testing procedure. Following standard practice, the audiologist may ask the participant to repeat or clarify their response if their initial response is deemed to be inaudible or unintelligible. Audio-visual recordings of the participant performing the test will be made and post-processed to occlude the devices worn by the participant. The resulting occluded recordings will be scored by two independent assessors who will be qualified audiologists with experience of administering and scoring clinical speech perception tests with patients with severe hearing losses. These independent assessors will be blinded to treatment arm and assessment timepoint. Disagreement in scores will be resolved by consensus, failing which a third independent assessor will adjudicate using the video recordings.

Secondary outcomes

- Secondary clinical outcome measures in this trial are:
- *Phoneme perception (AB Word test at 60 dBA) (3, 6 and 9 months following first treatment activation), assessed live by the audiologist*
- *Word perception (AB Word test at 60 dBA) (3, 6 and 9 months following first treatment activation)*
- *Phoneme perception (at 70 dBA) (9 months following first treatment activation)*
- *Word perception (at 70 dBA) (9 months following first treatment activation)*

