- These tests will be carried out as described for the primary outcome with the exception that only live scoring by the audiologist administering the test will be used and at 9 months a test at 70 dBA will be performed.
- *Sentence perception in quiet (3, 6 and 9 months following first treatment activation)*
Sentence perception in quiet will be assessed in the best-aided condition by administering the BKB sentence test (Bench et al., 1979). Sentences will be presented from a loudspeaker and the audiologist will determine the proportion of words repeated correctly by the participant. Different sentence lists will be used at each administration with no list presented more than once to the same participant. The test will be scored live by the audiologist administering the test with no feedback given to the participant at any point in the testing procedure.
- *Sentence perception in noise (3, 6 and 9 months following first treatment activation)*
Sentence perception in noise will be assessed in the best-aided condition by administering the BKB sentence test while a speech-shaped background noise is presented at the same time and from the same loudspeaker. The relative levels of speech and noise will be varied adaptively based on the accuracy of the participant's responses to estimate a speech reception threshold, defined as the signal-to-noise ratio at which participants can report 50% of sentences correctly. An accurately reported sentence is one in which all key words are repeated correctly by the participant. The test will be scored live by the audiologist administering the test with no feedback given to the participant at any point in the testing procedure.
- *Device usage (device logging)*
Statistics on device use will be obtained from the data logging features of the trial devices (CIs and HAs). The statistics will include the duration that the devices have been used and information about the nature of the acoustic environments in which the devices have been used. Data will be extracted from the trial devices directly at in-person assessments 3, 6, and 9 months following first treatment activation. Data could also be

downloaded using the standard remote capabilities of the devices, for those using the trial devices and where the participant chooses to use them.

Secondary participant-reported outcome measures in this trial are:

- *Self-reported difficulty with listening*

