The phoneme score (a measure of phoneme perception) on the AB word test presented at 60 dBA, in the best-aided condition (i.e., using the devices that the participant considers will help them hear as well as possible) at 9 months post first treatment activation measured by independent blinded assessors.	The phoneme score is the proportion of phonemes repeated correctly
Secondary Outcomes	
Phoneme score (phoneme perception using the AB Word test at 60dBA) at 3, 6 and 9 months post first treatment activation assessed live by an audiologist	The proportion of phonemes repeated correctly
Word perception (AB Word test at 60 dBA) at 3, 6 and 9 months post first treatment activation assessed live by an audiologist	The proportion of words repeated correctly
Phoneme perception (AB Word test at 70dBA) at 9 months post first treatment activation assessed live by an audiologist	The proportion of phonemes repeated correctly
Word perception (AB Word test at 70dBA) at 9 months post first treatment activation assessed live by an audiologist	The proportion of words repeated correctly
Sentence perception in quiet (BKB sentence test at 70 dBA) at 3, 6 and 9 months post first treatment activation assessed live by an audiologist	The proportion of key words repeated correctly
Sentence perception in noise (BKB sentence test) at 3, 6, and 9 months post first treatment activation assessed live by an audiologist	The signal-to-noise ratio at which 50% of key words are repeated correctly (speech reception threshold)
Device usage (device logging)	
The average hours of daily use and cumulative hours of use for the following periods:
 
 • First treatment activation to 3 months • 3 to 6 months • 6 to 9 months 
Average and cumulative usage will also be reported for the same periods for each characteristic of the acoustic environments captured by the trial devices

Device usage (participant self-report)	
The estimated average hours of daily use as reported by patients each month from first treatment activation to 9 months.
 
Cumulative hours of use from the patient-reported daily use estimates, for the following periods:
 
 • First treatment activation to 3 months

Outcome Measure	Derivation
	
 • 3 to 6 months • 6 to 9 months
Difficulty with listening	The mean SSQ12 score at 1, 3, 6, and 9 months.

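### The 9-month AB word score at 60 dBA is scored only by an unblinded audiologist, although two blinded assessors already score the recorded responses from the same test

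*Protocol*

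**What the plan says.** **Who scores the word test.** Under Trial Treatment and Regimen, Secondary outcomes, the AB tests other than the primary follow the primary's procedure, except that "only live scoring by the audiologist administering the test will be used". The outcome table under Assessment of performance repeats this: "Word perception (AB Word test at 60 dBA) at 3, 6 and 9 months post first treatment activation assessed live by an audiologist". It defines the score as "The proportion of words repeated correctly".

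**Who scores the primary.** The Blinding section says that the baseline and 9-month "measures of the primary outcome will also be video recorded and scored by two independent blinded assessors". The stated purpose is to minimise bias. The same section says that clinicians and treating staff cannot be blinded, because of the surgery and the visible difference between devices.

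**One test, two kinds of scorer.** The Primary outcome section says "The test will be scored live by the audiologist administering the test at all timepoints", and then: "Audio-visual recordings of the participant performing the test will be made and post-processed to occlude the devices worn by the participant". The Synopsis describes the live phoneme outcome as the "same test as primary outcome but assessed live by audiologist at 3, 6 and 9 months". The Blinding section adds: "The blinded scoring of the primary outcome at baseline and 9 months will form part of the trial datasets for analysis". It leaves the full blinded-scoring procedure to a separate working practice document.

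**Status of the outcome.** Under Statistics, Methods, all secondary analyses support the primary, and no multiplicity adjustment is made. The word score at 60 dBA nevertheless gets a between-arm comparison and a repeated-measures model.

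**The concern.** Live marking of spoken responses involves judgement about what was said. The protocol accepts that this can be biased when the scorer knows the arm, and guards against it for the phoneme score. The word score at the same visit comes from the same responses and gets no such protection, and no reason is given.

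For most of the other speech outcomes the omission has a practical explanation. Sentence tests, the 70 dBA test, and the 3- and 6-month visits would need further recordings and assessor time. That does not apply to the 60 dBA word score at 9 months, where everything needed is already planned.

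At stake is the credibility of one secondary comparison in an open trial of devices that participants and staff can see. Any tendency of live scorers to favour one arm would pass straight into the estimated difference and could not be told apart from a treatment effect.

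**Working it through.** **1. The plan's own figure.** From Sample size and justification: difference 15 points, SD 24, two-sided 5%, power 90%.

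- Normal approximation: n = 2 × (1.96 + 1.2816)² × 24² / 15² = 53.8, so 54 per arm.
- t-test version: 54.8, so 55 per arm, as stated.
- Allowing for 15% non-collection: 55 / 0.85 = 64.7, so 65 per arm and 130 in total, as stated.

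The sample size reproduces. It concerns the phoneme score, and a change of scorer for the word score leaves it alone.

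**2. Is it the same set of responses?** The primary test is scored live at every timepoint, and the recording is of the participant performing that test. Under Baseline Visit, each test is done once and may not be repeated, so at baseline the live and blinded scores must come from one administration. At 9 months the Primary outcome section describes a single test that is both scored live and recorded. A second administration is nowhere mentioned.

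**3. Can a blinded word score be obtained?** If assessors mark item by item, and a word counts as correct when all its phonemes are correct, the word score follows from the phoneme marks. Both conditions are reasonable, but the protocol states neither. It does not say whether item marks or only totals are kept, or at what level disagreements are settled.

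**4. Where can allocation bias arise?** Under Baseline Visit, randomisation follows completion of all baseline assessments. The baseline live scorer cannot know the arm, so the bias in question arises only after randomisation.

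**5. Size, as an illustration.** The protocol gives neither a scorer bias nor a word-score SD. Assumptions: true difference zero; 55 per arm; SD 24 borrowed from the phoneme score and varied from 18 to 30; live scoring shifts the difference between arms by b points.

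SE = SD × √(2/55). For SD 24, SE = 24 × 0.1907 = 4.58. For SD 18 it is 3.43, and for SD 30 it is 5.72.

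False-positive rate = P(Z > 1.96 − b/SE) + P(Z < −1.96 − b/SE).

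| Bias b (points) | SD 18 | SD 24 | SD 30 |
|---|---|---|---|
| 1 | 6.0% | 5.5% | 5.4% |
| 3 | 14.1% | 10.0% | 8.2% |
| 5 | 30.8% | 19.4% | 14.1% |

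The estimated difference itself moves by b, whatever the SD.

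**The case against.** **The outcome is supportive, and the same responses already have a blinded answer.** This stands. The primary phoneme score is blinded, double-scored and adjudicated, so a reader is not left without a protected result for this test at this visit. It limits the importance of the point, but does not explain leaving the word score unprotected.

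**Live scoring gives one method across 3, 6 and 9 months.** This also stands, and it is why the live series should be kept for the arm-by-time model. It does not prevent a blinded score from being used for the 9-month comparison.

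**Item-level marking is not stated.** Correct. A reader might infer that a blinded word score already exists. The protocol does not support that, because the detail lies in a working practice document that is not shown. The fix must therefore ask for item-level marks.

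**The proposed change leaves more exposed outcomes untouched.** True for the sentence tests, the 70 dBA test, and the 3- and 6-month AB tests. Nor does blinded scoring remove influence at administration: the unblinded audiologist may ask for an unclear response to be repeated.

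**The double-scored phoneme data are not wasted.** A reader might infer that no use of them is planned. In fact the 9-month phoneme score is a listed outcome in both its blinded and live forms. A formal comparison of the two may be in the statistical analysis plan, which was not available, so its absence from the protocol is not a defect.

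**Conclusion.** The point holds, limited to the 60 dBA word score at 9 months. Scorer bias is left in a supportive secondary outcome where it could be avoided with no new recordings, visits or assessors.

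Three stronger readings are not supported:

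- That this is a key secondary outcome. The protocol ranks none of them.
- That the protocol contradicts itself or puts the primary result at risk. Live scoring is stated openly and consistently, and the primary analysis uses blinded scores.
- That baseline scores are biased by arm. They are taken before randomisation.

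The size is unknown. The 5.5%, 10% and 19% for biases of 1, 3 and 5 points rest on assumed biases and a borrowed SD. Across SDs of 18 to 30 the ranges are 5.4 to 6.0%, 8.2 to 14.1% and 14.1 to 30.8%. They show how modest scorer drift would affect inference and do not predict that it will occur.

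**What to change.** 1. In Secondary outcomes under Trial Treatment and Regimen, and in the outcome table under Assessment of performance, state that the 9-month between-arm comparison of the 60 dBA word score uses the blinded assessors' scoring. Align the matching sentence on live scoring in the Trial Design section.
2. In the working practice document for blinded scoring, require marks to be recorded by item, and state the rule by which a word counts as correct, so that whole-word scores can be derived.
3. The blinded baseline word score may serve as the covariate, so that baseline and outcome share a scorer. This is for consistency, not to remove allocation bias.
4. Keep live word scores at 3, 6 and 9 months for the repeated-measures model.
5. Optionally, report live minus blinded phoneme score by arm at 9 months, with a 95% confidence interval, as a check on the outcomes that remain live-scored.

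**Cost.** Wording, item-level recording and a derived variable. If any recordings have already been scored with only totals kept, those would need rescoring. The trial would also report two 9-month word scores, so the plan should say which one is used for which analysis.
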